## LIST OF ABBREVIATIONS

<List commonly used abbreviations/acronyms>

<RAI>	<Radioactive Iodine>
<RP>	<Renal Profile>
<LFT>	<Liver Function Test>
<TFT>	<Thyroid Function Test>
<ATD>	<Antithyroid Drug>
<CMZ>	<Carbimazole>
<TED>	<Thyroid Eye Disease>
<SAE>	<Serious Adverse Events>
<AE>	<Adverse Events>

## RESEARCH SYNOPSIS

Study Title	A randomized controlled trial on the effectiveness of lithium in comparison to carbimazole as a bridging therapy prior to radioactive iodine for hyperthyroidism.
Objective	
Primary To assess the proportion of cure at 6months of radioactive iodine between those who were pre-treated with lithium versus carbimazole.
 
Secondary To assess change in serum thyroid hormone levels following two months of lithium versus carbimazole therapy prior to the administration of radioactive iodine.

Study Designs	A prospective randomized controlled, open label, single centre study. Subjects will be randomized into lithium or carbimazole arms in a 1:1 ratio. Lithium arm will receive tab Lithium Carbonate 300mg OD while Carbimazole arm will receive tab Carbimazole 10mg OD for a duration of two months prior to radioactive iodine treatment.
Study Endpoints / Outcomes	Changes in the thyroid hormone levels at 2 months of treatment and at months 1,3 and 6 following radioactive iodine.
Study Population	All adult patients who are 18 years and above with hyperthyroidism either newly diagnosed or relapse disease secondary to Graves' Disease, toxic multinodular goitre and toxic adenoma who are planned for radioactive iodine therapy as a definitive treatment from 18/12/2020 till 31/12/2021 at Pusat Perubatan Universiti Kebangsaan Malaysia.
Inclusion / Exclusion Criteria	
Inclusion Criteria
 
 
• Adult patients aged 18 years old and above with thyrotoxicosis who have been planned for definitive RAI: 
 
○ consented for radioactive therapy as a definitive treatment.
 
○ able to comply with requirement of radioiodine therapy.
 
○ FT4 level below 40pmol/L.
 
 
 
 
Exclusion Criteria
 
 
• Pregnancy or Lactating mother
 
• Moderate to severe and active thyroid eye disease based on EUGOGO criteria, requires steroid cover
 
• Renal impairment, egfr <45ml/min (stage 3b)
 
• Underlying active malignancy
 
• Underlying active schizophrenia or bipolar disorder
 
• Patients on medications that may interact with lithium (refer to APPENDIX 1)
 
• Patients on medications that may interfere with RAI effectiveness: 
 
○ Amiodarone
 
○ Less than a month of intravenous contrast medium
 
 
 
• Previous RAI < 6months
 
• Previous history of adverse effect following exposure to lithium or carbimazole.
 
• Thyroid carcinoma
 

Sample Size	86 subjects
Study Duration	18/12/2020 – 31/12/2021

## BACKGROUND AND SIGNIFICANCE

Hyperthyroidism is a state of overactive thyroid gland due to autoimmune Graves' Disease, toxic multinodular goitre or toxic adenoma. Radioactive iodine (RAI) therapy is a common treatment modality for hyperthyroidism either as primary treatment or after failure of medical treatment. The aim of radioactive iodine therapy is a stable restoration to euthyroid state, however, a substantial proportion of patients become hypothyroid.

Although generally safe, radioiodine therapy has some potential side effects include gastrointestinal symptoms, radiation thyroiditis, sialadenitis/xerostomia, bone marrow suppression, gonadal damage and pulmonary fibrosis. Therefore it is pivotal to render cure in patients who are undergoing radioactive iodine at the first attempt to minimize the unwanted adverse effects.

Cure rate within a year post RAI is around 72%, however cure rates seems to differ from centre to centre. Several factors have been found to affect the success of RAI therapy and some of the known ones are prior use of thionamide, hyperthyroid state, gender, dose of RAI, RAI uptake and retention of RAI in the thyroid gland.

Simultaneous use of antithyroid drug (ATD) with RAI has consistently been shown to result in lower efficacy and higher failure rate than treatment with RAI alone. Antithyroid drug have a radioprotective effect and pre-treatment with ATD has been shown to increase the risk of treatment failure with subsequent RAI. The result is consistent even if the drugs are discontinued 4-7 days before RAI therapy. Carbimazole (CMZ) is the current standard therapy in the management of hyperthyroidism prior to radioactive iodine therapy. Connell *et al.*, reported that CMZ stopped 5 days before RAI reduced the rate of hypothyroidism at 1-year compared to non-pretreated patients. There are two other studies that have reported CMZ pre-treatment reduced the efficacy of RAI therapy. In a meta-analysis of 14 randomized controlled trials, adjunctive ATD, including CMZ, was associated with an increased risk of treatment failure with RAI. Despite these evidences, ATD are still being given in clinical practice prior to RAI in an attempt to avoid thyroid storm associated with high levels of thyroid hormones prior to RAI administration.

It is important to note that since Malaysia do not produce its own RAI and has to imported from overseas there will always be a significant waiting period. The waiting period may range between 2-3months in most of the centres including in Pusat Perubatan Universiti Kebangsaan Malaysia. In the past, patients would be continued on the usual ATD until 3days before the administration of RAI. Unfortunately, the ongoing use of ATD continued until prior to RAI may result in lowering of the RAI uptake and thus reduce the efficacy of RAI therapy. This is where an alternative bridging therapy with lithium may offer a better alternative especially in terms of RAI uptake.

Lithium has been shown not to interfere with the RAI uptake. In fact, some studies demonstrated lithium improves the success rate of RAI. Lithium plays multiple roles in thyroid hormone synthesis process. Lithium inhibits the coupling of iodotyrosine residues to form iodothyronines thyroxine (T4) and triiodothyronine (T3), and inhibits release of T4 and T3. Lithium blocks the release of organic iodine from the thyroid gland, therefore it is able to increase RAI retention in the thyroid and does not interfere with thyroidal RAI uptake.

Lithium use in treating hyperthyroidism has not been used widely due to its potential adverse effects including a spectrum of central nervous system, cardiovascular, and renal side effects namely confusion, coma, seizures, ventricular irritability, sinus node dysfunction, sinoatrial block, nephrogenic diabetes insipidus and electrolyte imbalance. However these adverse effects associated with higher doses of lithium. In this particular study a very low dose of lithium (300mg daily) will be used. Previous studies showed that the occurrence of significant side effects of lithium was low with lower doses. The study by Bal et al used a dose of 300mg three times daily for 21 days did not demonstrate any severe adverse effects and only a small group of patients experienced mild gastrointestinal symptoms.

Currently hyperthyroidism is mainly being treated with medical therapy using carbimazole for a duration of 12 to 18 months duration. However, the relapse rate can be as high as 80% following cessation of ATD due to the nature of the disease. Hence, some patients will need RAI as a definitive treatment because it is a well-known fact that another course of ATD in this kind of patients will not render cure. In certain patients, eg those with thyrotoxic cardiomyopathy or hypokalaemic periodic paralysis RAI would be a primary treatment because it is important to render cure in these subset of patients to avoid cardiovascular sequelae.

In view of the waiting period to receive RAI, most patients will be pre-treated with ATD prior to RAI. However, some patients may develop side effects towards carbimazole such as liver impairment, allergic reaction or agranulocytosis. In this respect, lithium is being used as an alternative treatment. To the best of our knowledge there are no head to head study comparing lithium versus carbimazole as the pre-treatment medications prior to RAI. This would be the first study to explore the effects of the two medications prior to RAI and the novelty of this study would shed some insights into their roles and clinical applicability as well as filling up the gaps of the current literature.

## **HYPOTHESES**

In relation to the overall objective, the following are the hypotheses:

- Lithium resulted in higher proportion of cure compared to carbimazole at 6 months of radioactive iodine.
- Lithium resulted in comparable thyroid hormone levels as carbimazole at two months following treatment prior to RAI administration.

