### Secondary

To assess change in serum thyroid hormone levels following two months of lithium versus carbimazole therapy prior to the administration of radioactive iodine.

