## **METHODOLOGY**

### Study Design

This is a prospective randomized, open label, single center interventional study comparing the effectiveness of lithium versus carbimazole in lowering the thyroid hormone levels in patients undergoing radioactive iodine.

Patients will be randomized into lithium or carbimazole arms in a 1:1 ratio. Patients will receive either lithium carbonate 300mg once daily or carbimazole 10mg once daily, which is the current standard therapy. The necessary precautions will be given with regards to the study drugs. Patients will be on the above treatment for a duration of 2 months and carbimazole will be stopped 3 days prior to radioactive iodine treatment whereas lithium will be discontinued on day 3 post RAI as per usual practice. RAI will be administered at a fixed dose of 15mCi in both groups.

Antithyroid drug (ie. Methimazole or carbimazole) is restarted if needed (in symptomatic patients with FT4 of more than 40 pmol/L) at least a week after radioactive iodine and titrated as per standard treatment protocol.

Patients are declared to be cured at the end of 6 months based on thyroid function test and requirement of treatment either with thyroxine or antithyroid drug.

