### Assays and values

#### *Thyroid Function Test*

Thyroid Stimulating Hormone (TSH) and Free T4 (FT4) are measured using Chemiluminescent Microparticle Immunoassay (CMIA) method.

The normal range for TSH is 0.35-4.94 uIU/ml and for FT4 is 9-19.05 pmol/L.

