## Statistical Analysis Plan

Data will be entered and analysed using SPSS version 23 with appropriate statistical tools. Normally distributed data will be presented as mean $\pm$ SD. Non-normally distributed data will be presented as median and interquartile range. For comparison of baseline characteristics between the two groups, (lithium vs carbimazole) the independent sample t-test will be used if the numerical data is normally distributed and the Mann-Whitney U-test for non-normally distributed data. Pearson's Chi-square test will be used to compare the categorical data between the two groups (lithium vs carbimazole).  $P < 0.05$  will be used to determine statistical significance; data reported as mean Standard Deviation.

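### The secondary hypothesis claims comparable two-month hormone levels, but the protocol sets no margin or interval criterion, and its only rule (P < 0.05) can contradict that claim but never support it

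*Protocol*

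**What the plan says.** The Hypotheses section lists two hypotheses. The first is that lithium gives a higher cure proportion at 6 months. The second is that "Lithium resulted in comparable thyroid hormone levels as carbimazole at two months following treatment prior to RAI administration".

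The matching secondary objective is neutral: "To assess change in serum thyroid hormone levels following two months of lithium versus carbimazole therapy prior to the administration of radioactive iodine".

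The protocol's Statistical Analysis Plan section gives the following for numerical data: "For comparison of baseline characteristics between the two groups, (lithium vs carbimazole) the independent sample t-test will be used", with the Mann-Whitney U-test if the data are not normal. Pearson's chi-square test covers categorical data. The only criterion is that P < 0.05 "will be used to determine statistical significance". Strictly, no test is assigned to the two-month hormone levels.

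The only hypotheses written out formally, in the Sample Size section, concern equality of the two cure proportions. The protocol contains no margin, no equivalence or non-inferiority test, and no confidence-interval criterion for hormone levels.

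**The concern.** A test for a difference asks whether the data are incompatible with no difference. When P exceeds 0.05 the arms may be similar, or the trial may be too small or too variable to tell. If the hypothesis is similarity and the only rule is P < 0.05, the rule can reject the hypothesis but cannot confirm it. The incentive also runs the wrong way: the less precise the trial, the more likely its result is to leave *comparable* uncontradicted.

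The outcome is not incidental. Study Design describes the whole trial as "comparing the effectiveness of lithium versus carbimazole in lowering the thyroid hormone levels in patients undergoing radioactive iodine". The synopsis lists "Changes in the thyroid hormone levels at 2 months of treatment" under endpoints. Background and Significance explains that antithyroid drugs are given before radioactive iodine (RAI) "in an attempt to avoid thyroid storm associated with high levels of thyroid hormones prior to RAI administration". A reader deciding whether lithium can take carbimazole's place as a bridge will look for exactly this result. A report that levels were comparable because P exceeded 0.05 could hide a sizeable difference in hormone control.

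**Working it through.** **1. The plan's own figure.** The Sample Size section uses cure proportions 0.91 and 0.57, two-sided alpha 0.05 and power 0.90:

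(1.96·√0.385 + 1.29·√0.327)² / 0.34² = (1.216 + 0.738)² / 0.1156 ≈ 33.0

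With the protocol's rounded inputs this is 33.02, which rounds up to the stated 34. Unrounded normal quantiles give 32.85, so 33. Allowing 20% dropout, 34/0.8 = 42.5, so 43 per arm. The figure reproduces, but it covers only the difference in cure. Nothing in the protocol sizes the hormone comparison.

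**2. Inputs for the hormone comparison.** I take 34 to 43 evaluable patients per arm at two months, that is, with full dropout or none. The protocol gives no SD and no relevant difference, so results are in SD units and assume roughly normal data with equal SDs.

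**3. Precision.** The 95% CI half-width is t(0.975, 2n−2)·√(2/n):

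- n = 34: 1.997 × 0.2425 = 0.484 SD
- n = 43: 1.989 × 0.2157 = 0.429 SD

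For scale, the protocol's reference range "for FT4 is 9-19.05 pmol/L" is 19.05 − 9 = 10.05 pmol/L wide. If the FT4 SD were 4, 6 or 8 pmol/L (assumed), the half-width at 34 per arm would be 1.9, 2.9 or 3.9 pmol/L, which is 19%, 29% or 39% of that width.

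**4. How often a real difference gives P > 0.05** (two-sided noncentral t, noncentrality d/√(2/n)):

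| True difference | n = 34 per arm | n = 43 per arm |
|---|---|---|
| 0.3 SD | 1 − 0.230 = 77% | 1 − 0.280 = 72% |
| 0.5 SD | 1 − 0.529 = 47% | 1 − 0.630 = 37% |

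If the arms are truly equal, P < 0.05 still occurs 5% of the time. A simpler normal approximation gives 76% and 72% for 0.3 SD, and 46% and 36% for 0.5 SD.

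**5. What a proper comparability claim would need.** This is the margin giving 80% power when the true difference is zero, averaging over the sampling distribution of the SD:

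| Criterion | Unadjusted, n = 34 / 43 | Baseline-adjusted, r = 0.5, n = 34 / 43 |
|---|---|---|
| Two-sided 95% CI within ± margin | 0.80 / 0.71 SD | 0.69 / 0.61 SD |
| 90% CI within ± margin | 0.72 / 0.64 SD | 0.62 / 0.55 SD |
| Upper 95% limit only | 0.69 / 0.61 SD | 0.60 / 0.53 SD |

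The adjusted column uses residual SD √(1 − r²) = √0.75 = 0.866 and 2n − 3 degrees of freedom, where r is the assumed correlation between baseline and two-month values. The last row suits FT4, where a higher lithium level is the unfavourable direction. For TSH the direction reverses.

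**The case against.** The strongest reply is that this is an omission, and that a separate SAP may supply the margin and model. The protocol's t-test sentence is written for baseline characteristics, so its analysis section is arguably silent on the two-month levels and does not contradict the hypothesis. No sentence says that P > 0.05 will be read as comparable. The secondary objective and the Study Design text are neutral, so only one bullet is out of line, and *comparable* may be an informal expectation. The figures rest on assumed SDs and on normality, although the protocol itself foresees non-normal data. Baseline adjustment improves precision but does not cure the defect.

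Much of this is fair. It is true that no test is assigned to this outcome, that no rule equates non-significance with comparability, and that baseline adjustment is a separate efficiency recommendation. The point survives because the hypothesis is the protocol's own, one of only two, and the one criterion the protocol states cannot establish it. A SAP could add detail, but the claim would still be stated more strongly than the protocol's own objective and criterion allow. The assumed SDs affect only the pmol/L illustration. The logical gap does not depend on them.

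**Conclusion.** The concern holds. The hypothesis asserts similarity, the objective is neutral, and the only stated criterion addresses difference. Results in SD units rest on 34 to 43 evaluable patients per arm and approximately normal data. On that basis the trial would miss a true 0.5 SD difference in roughly two-fifths to one-half of cases, and a 0.3 SD difference in about three-quarters. Whether differences of that size matter clinically is for the investigators to say.

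This is a secondary hypothesis, and the primary endpoint, sample size and visit schedule stand as they are. It should be corrected before analysis, but it does not undermine the trial.

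**What to change.** **Simplest route.** Reword the second hypothesis to agree with the secondary objective, for example: to estimate the lithium-minus-carbimazole difference in two-month hormone levels, with a 95% CI. Add one sentence that P > 0.05 will not be read as comparability.

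**If the claim is kept.** State a margin that the investigators justify, fix it before analysis, and claim comparability only if the CI lies within it. Say which interval is used and, if the criterion is one-sided, which direction is unfavourable for FT4 and for TSH.

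**On either route (recommended, separate from the defect).** Analyse two-month FT4 by ANCOVA with arm and baseline FT4, and report the adjusted difference with its 95% CI. Treat TSH the same way, transformed if skewed. With baseline as covariate, the adjusted difference in level and in change is the same, so this also fits the objective's wording. The variance reduction depends on r, which is assumed:

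- Against a change score, the ratio (1 − r²)/(2 − 2r) is 0.65, 0.75 or 0.85 for r = 0.3, 0.5 or 0.7, a saving of 35%, 25% or 15%.
- Against raw two-month levels, the ratio 1 − r² is 0.91, 0.75 or 0.51, a saving of 9%, 25% or 49%.

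**Cost.** One reworded line and one standard SPSS model. Thyroid function is already measured at recruitment and on the RAI day, so no extra patients or visits are needed. The downside is that comparability may not be claimable at this size, because without adjustment a margin of about 0.6 to 0.8 SD is needed for 80% power, depending on the criterion. That is better known before the data are analysed.

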## **OBJECTIVES**

### Primary

To assess the proportion of cure at 6 months of radioactive iodine between those who were pre-treated with lithium versus carbimazole.

### Secondary

To assess change in serum thyroid hormone levels following two months of lithium versus carbimazole therapy prior to the administration of radioactive iodine.

## **METHODOLOGY**

### Study Design

This is a prospective randomized, open label, single center interventional study comparing the effectiveness of lithium versus carbimazole in lowering the thyroid hormone levels in patients undergoing radioactive iodine.

Patients will be randomized into lithium or carbimazole arms in a 1:1 ratio. Patients will receive either lithium carbonate 300mg once daily or carbimazole 10mg once daily, which is the current standard therapy. The necessary precautions will be given with regards to the study drugs. Patients will be on the above treatment for a duration of 2 months and carbimazole will be stopped 3 days prior to radioactive iodine treatment whereas lithium will be discontinued on day 3 post RAI as per usual practice. RAI will be administered at a fixed dose of 15mCi in both groups.

Antithyroid drug (ie. Methimazole or carbimazole) is restarted if needed (in symptomatic patients with FT4 of more than 40 pmol/L) at least a week after radioactive iodine and titrated as per standard treatment protocol.

Patients are declared to be cured at the end of 6 months based on thyroid function test and requirement of treatment either with thyroxine or antithyroid drug.

### Randomization

Block randomization method will be utilised to randomize subjects into the two groups by selecting treatment arm from a box consisting of 8 options (4 lithium and 4 carbimazole). Once the box is empty, it will replenished by the same 8 options.

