### Study Population

All adult patients who are 18 years and above with hyperthyroidism either newly diagnosed or relapse disease secondary to Graves' Disease, toxic multinodular goitre and toxic adenoma who are planned for radioactive iodine therapy as a definitive treatment will be included in this study.

The study period is from 18/12/2020 till 31/12/2021 at Pusat Perubatan Universiti Kebangsaan Malaysia.

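### Randomisation uses one unstratified box although antithyroid drug use at entry is unregulated and the protocol calls it prognostic; recording it and adding a second box is a cheap improvement

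*Protocol*

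**What the plan says.** **Allocation.** Study Design: "Patients will be randomized into lithium or carbimazole arms in a 1:1 ratio". Randomization: "Block randomization method will be utilised to randomize subjects into the two groups by selecting treatment arm from a box consisting of 8 options", four per arm, with the box refilled when empty. No stratification factor is named.

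**Who enters.** Study Population admits "hyperthyroidism either newly diagnosed or relapse disease". Apart from the diagnosis itself, the only thyroid-function limit in the Inclusion Criteria is FT4 below 40 pmol/L. Neither the Exclusion Criteria nor Appendix 1 mentions current ATD use, and no washout or run-in is described.

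**ATD in practice.** The Background reports that patients at this centre used to stay on their usual ATD until 3 days before RAI. It adds that, because of the wait for RAI, "most patients will be pre-treated with ATD prior to RAI". It also describes some patients for whom RAI is the primary treatment.

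**ATD as a prognostic factor.** Of the factors affecting RAI success, the Background says "some of the known ones are prior use of thionamide", ahead of several others. It adds that "pre-treatment with ATD has been shown to increase the risk of treatment failure with subsequent RAI".

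**Outcomes and analysis.** The primary outcome is cure 6 months after RAI, tested by an unadjusted Pearson chi-square (Sample size). The secondary objective is the change in thyroid hormone over two months, with comparable levels hypothesised. Study Visits and Procedures requires a history at recruitment but does not name ATD use as an item.

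**The concern.** ATD status at entry changes what the randomised comparison means. In an untreated patient, the trial compares no thionamide before RAI with about two months of it. In a patient already on ATD, it compares stopping the thionamide about two months before RAI with continuing it until 3 days before. Thionamide exposure ahead of RAI is the protocol's own rationale for the trial, so these are different contrasts.

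The secondary outcome is the more exposed. A baseline FT4 measured on ATD is a suppressed value; one measured off ATD is not. The two-month change can differ in size, and possibly in direction, between the groups. A pooled change near zero could then be read as support for comparable levels when it averages unlike changes. Adjusting for baseline FT4 does not settle this, since the same value can be treated in one patient and untreated in another.

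For the primary outcome, a factor the protocol treats as prognostic is left to chance between two arms of 43.

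**Working it through.** **1. The plan's own sample size.** Inputs from Sample size: cure 0.91 and 0.57, two-sided alpha 0.05, power 0.90, 20% dropout.
- Protocol's rounded terms: (1.96 × √0.385 + 1.29 × √0.327)² / 0.34² = 33.02, rounded up to 34.
- Unrounded z values: 32.85, rounded up to 33.
- Dropout: 34 / (1 − 0.20) = 42.5, rounded up to 43 per arm, 86 in total.

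The stated 34 and 43 are reproduced. Stratifying does not alter them.

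**2. Chance imbalance under one box.** The protocol gives no figure for the share q on ATD at entry, so 30%, 50% and 70% are assumed.
- Formula: SD of the between-arm difference in share = √(2q(1 − q)/43).
- q = 0.5: √(0.5/43) = 0.108. q = 0.3 or 0.7: √(0.42/43) = 0.099.

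Simulating 20,000 trials of 86 patients in unstratified blocks of 8 agrees:

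| Assumed share on ATD | Mean gap | SD (points) | Gap ≥ 15 points | Gap ≥ 20 points |
|---|---|---|---|---|
| 30% | 0 | 9.8 | 13% | 4% |
| 50% | 0 | 10.8 | 16% | 7% |
| 70% | 0 | 9.9 | 13% | 4% |

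**3. What a 20-point gap would do to cure.** Shift = imbalance × difference in cure between ATD groups. For assumed differences of 10, 20 and 34 points: 0.20 × 10 = 2, 0.20 × 20 = 4, and 0.20 × 34 = 6.8 points. The standard error of the planned comparison at 34 per arm is √((0.91 × 0.09 + 0.57 × 0.43)/34) = √(0.327/34) = 9.8 points, so a 4-point shift is about 0.4 of a standard error.

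**4. What mixing could do if the effect differs.** As a deliberately extreme assumption, let the planned 34-point gain exist in only part of the patients and be zero in the rest. Power is at 34 per arm, from the protocol's formula solved for power.

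| Share with the full gain | Pooled difference | Power |
|---|---|---|
| 100% | 34 points | 91% |
| 70% | 0.70 × 34 = 23.8 points | 57% |
| 50% | 0.50 × 34 = 17 points | 31% |
| 30% | 0.30 × 34 = 10.2 points | 14% |

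**5. What a stratum can show alone.** With the full 34-point gain in a stratum holding 30%, 50% or 70% of 34 per arm (10.2, 17 or 23.8 patients per arm), power is 41%, 63% or 78%.

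**6. FT4 illustration.** Suppose half the lithium arm is untreated at entry and falls by 10 pmol/L, and half is switched and rises by 5 (both assumed). The lithium-arm mean is 0.5 × (−10) + 0.5 × 5 = −2.5. This is a within-arm mean, not the lithium–carbimazole difference. It shows why the change needs to be seen by ATD status.

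**The case against.** The strongest reply is that randomisation already does its job. Both arms draw on the same mix, the expected imbalance is zero, and the test's type I error allows for chance imbalance. Unstratified permuted blocks are a valid choice for 86 patients. All of this stands.

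A reader might infer that the pooled result can describe neither group, or that the single box causes the problem. The documents support neither reading. The pooled contrast is a valid average over those enrolled, and it describes both groups if the effect is similar in each. With two boxes it would still be an average: stratifying removes chance imbalance, not mixing. The root gap is that ATD status at entry is left undefined.

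The evidence for the mix is also indirect. "either newly diagnosed or relapse disease" is not the same as untreated or on drug, since the Background describes relapse after ATD has been stopped. The remark about most patients being pre-treated concerns the waiting period, which is the window this trial randomises. Much of the Background evidence concerns ATD given with RAI or stopped a few days before, which is the randomised contrast. It does not show a separate effect of a thionamide stopped two months earlier. These points limit the certainty, but nothing in the criteria excludes either group.

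Finally, adjustment and subgroup reporting can be left to an analysis plan, which is not at hand. That plan could not change the randomisation, however, and could use ATD status only if it had been recorded.

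**Conclusion.** The point holds as a cheap improvement, not as a flaw that invalidates the trial. The protocol leaves ATD status at entry undefined, does not name it as a baseline item, and does not balance it, while calling earlier thionamide use a factor in RAI success.

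Chance imbalance is modest: an SD of about 10 to 11 points, and a gap of 20 points or more in about 4% to 7% of trials. At that gap the cure difference moves by about 2 to 7 points, against a planned 34. The larger issue is interpretation. If the effect differs by ATD status, the pooled comparison may represent neither group well, and the two-month FT4 change is the more exposed outcome.

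The 30% to 70% shares, the 10- to 34-point prognostic differences, the zero-effect scenario and the FT4 changes are all assumptions. The documents give no such figures and do not state that enrolled patients are on ATD.

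**What to change.** - **Record:** make thionamide use at randomisation a named item of the baseline history in Study Visits and Procedures.
- **Randomise:** keep two boxes of 8 (four per arm in each), one for patients on a thionamide and one for the rest.
- **Analyse:** include the stratum, with Cochran-Mantel-Haenszel for 6-month cure and a stratum term for the two-month FT4 change.
- **Report:** show both outcomes by stratum as descriptive only, since power within a stratum is about 41% to 78%.

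The cost is a second box and a short amendment. The downside is one more incomplete last block, with an imbalance of at most 4 patients within it. The second stratum would still combine never-treated patients with those who stopped earlier, so the date of last use is worth recording in the same history. No extra patients or visits are needed, and 34 and 43 per arm stand.
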